### 7.2.1. Electronic Diary

Patients will be issued an eDiary to record all bleeding events and all doses of BPAs administered during the conduct of the study. Entries are to be made in a timely manner, and it is preferred that doses are entered immediately upon administration or within 24 hours. Patients will be prompted to enter bleeding location, severity, causality (spontaneous or traumatic), doses of bypass agents, and reasons for dosing (prophylaxis, treatment of a bleed, and preventive dose for anticipated activity). Training of patients should be documented in the appropriate source record.

The Sponsor or an independent delegate will review diary entries for data quality to identify issues such as subjects who may need retraining on diary use and timely entry of bleeding episode information.

Bleeding episodes will be recorded by the patient in the eDiary, and reviewed by the Investigator (and Sponsor or independent delegate) continuously for the study duration. The site will contact the patient at a minimum interval of every 2 weeks per schedule of assessments to review diary records and ensure that the patient is utilizing the device appropriately.

Sites will be notified when patients enter initial treatments for bleeding events into their eDiaries. If the dose amount exceeds the recommended dose according to the bleeding episode management plan, the patient must be contacted as soon as possible, preferably within 24-48 hours of receiving the alert. At the time of contact the patient's clinical condition will be reviewed along with the dose and efficacy of the treatment given, and the Investigator will provide appropriate guidance regarding further management of the bleeding episode. The site will also receive an alert, and must make contact with the patient as soon as possible if a third dose of product is administered for a single bleed, to review clinical condition, the need for further therapy, and appropriate ongoing management of the bleeding episode required to achieve hemostasis.

In addition, patients will be instructed to contact the site if they feel they need to administer BPA at a higher dose level or higher frequency than their bleeding episode management plan recommends, or if more than two doses are required to achieve hemostasis.

Complete instructions will be provided in the Study Manual.

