#### **6.3.1.1. Bleeding Episode Management Recommendations for Patients in the On-Demand Treatment Arm (Patients Not Receiving Fitusiran)**

For patients not receiving fitusiran (on-demand arm), bleeding management therapy with BPAs will be managed based on the local standard practice for treating hemophilia patients with inhibitors, as routinely administered by the physician. Where clinical circumstances allow, it is recommended that the patient contact the Investigator for all events that may be suspected to be or are characteristic of a bleeding episode. If adequate hemostasis does not occur after two doses of BPA, the patient should contact the site for further instruction. If the patient feels the need to administer doses higher than the patient's bleeding episode management plan recommends, or at a higher frequency, it is recommended that the patient contact the site. See Section 7.2.1 regarding patient use of the eDiary and site alerts that will assist in this process.

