**Bleed Management Guidelines Day 8 and Beyond:**

When a patient experiences symptoms that may be consistent with bleeding episodes, the following steps should be followed:

1. Patient should be instructed to call the study center to discuss symptoms to determine whether or not they are consistent with a bleeding event and to discuss the appropriate factor/BPA dose to use. This interaction between patient and Investigator is recommended prior to the administration of each dose of factor or BPA. Confirmation of bleeds at the study center prior to treatment may be considered. Such visits should capture assessments per Section 6.4 and Table 2.
2. If a determination is made that symptoms require treatment, the recommended treatment algorithm for bleeding episodes is described below:
  1. A single dose can be administered according to the guidelines in Table 4.
  2. The patient should be instructed to re-evaluate symptoms in 24 hours for bleeds treated with FVIII, FIX or aPCC and in 2-3 hours for bleeds treated with rFVIIa.
    - a. Administration of FIX Extended half-life should not be more frequent than every 5-7 days.
  3. If a second dose (in the case of FVIII, FIX or aPCC) or a third dose (in the case of rFVIIa) is needed, the patient must call the study center before dosing.
    - a. Consider evaluation and treatment of the patient at the study center and confirmation of bleeds when any repeated doses are needed (See Section 6.4 and Table 2).
    - b. If more than two doses of FVIII, FIX or aPCC or three doses of rFVIIa are needed, the patient should be seen at the study center within 48-72 hours.
  4. Doses should not be administered at less than 24 hour intervals (except rFVIIa as indicated in Table 4).

5. Doses should not exceed the protocol maximum recommended dose indicated in [Table 4](#).
6. Consultation with the study Medical Monitor and Clinical Advisor should be considered for clinical circumstances below, that may warrant AT replacement:
  - a. Doses of factor or BPA higher than those recommended in [Table 4](#)
  - b. Dosing of factor or BPA at decreased intervals than those recommended in [Table 4](#)
  - c. Multiple or repeated doses of factor or BPA
7. Antifibrinolytics may not be used in combination with factor or BPA.

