**Table 4: Bleed Management Dosing Guidelines by Specific Product**

	Factor VIII	Factor IX Standard half- life	Factor IX Extended half- life	aPCC	Recombinant Factor VIIa
Recommended single dose of	10 IU/kg	20 IU/kg	20 IU/kg	30 U/kg	≤45 µg/kg
Single Dose should not exceed	20 IU/kg	30 IU/kg	30 IU/kg	50 U/kg	45 µg/kg
Repeat dose instructions	Mandatory to call the clinical study center prior to second dose Consider evaluation and treatment at the clinical study center (see Section 6.4)				Mandatory to call site prior to third dose
	Should not repeat in less than 24 hours	Should not repeat in less than 24 hours	Should not repeat in less than 5-7 days	Should not repeat in less than 24 hours	Should not repeat in less than 2 hours
	Should be seen at site within 48-72 hours if more than 2 doses are required (see Schedule of Assessments for assessments)				Should be seen at site within 48-72 hours if more than 3 doses are required
For situations requiring higher doses, more frequent administration, multiple repeated doses, discussion with study Medical Monitor and Clinical Advisor is recommended, and AT replacement should be considered.					
Do not use antifibrinolytics in combination with factor or BPA.					

Note: Doses of FVIII and FIX are included for completeness. It is expected that these inhibitor patients will be routinely managed with rFVIIa or aPCC for bleeding episodes. Adjunctive management of bleeding episodes should be carried out per standard of care.

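### For the fitusiran arm from Day 8, the eDiary section sets patient contact at more than two doses, while Section 6.3.1.2 and Table 4 require a call before the second dose of FVIII, FIX or aPCC

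*Protocol*

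**What the plan says.** Protocol Section 7.2.1 (Electronic Diary) applies to every patient in the trial. Its last instruction to patients is to contact the site if they feel they need a higher BPA dose or frequency than their plan recommends, "or if more than two doses are required to achieve hemostasis". On alerts it says: "Sites will be notified when patients enter initial treatments for bleeding events into their eDiaries". If the amount entered exceeds the plan, the site must contact the patient. A further alert goes to the site "if a third dose of product is administered for a single bleed".

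The bleed management rules are in Section 6.3.1. For the on-demand arm, Section 6.3.1.1 says: "If adequate hemostasis does not occur after two doses of BPA, the patient should contact the site for further instruction".

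For the fitusiran arm from Day 8, Section 6.3.1.2 sets the trigger by product: "If a second dose (in the case of FVIII, FIX or aPCC) or a third dose (in the case of rFVIIa) is needed". What it then requires is that "the patient must call the study center before dosing". Table 4 has the same split. For FVIII, both FIX types and aPCC it says "Mandatory to call the clinical study center prior to second dose"; for rFVIIa it says "Mandatory to call site prior to third dose".

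Section 6.3.1 adds that FVIII and FIX doses are listed for completeness and that these inhibitor patients are expected to be managed with aPCC or rFVIIa.

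**The concern.** One protocol gives fitusiran-arm patients two different points at which to contact the site about a repeat dose of the same product. The later point is in the section that describes diary instructions and site alerts. The earlier point is in the section on bleed treatment.

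Repeat dosing under lowered antithrombin is a situation the protocol itself treats as sensitive. Section 6.5 says that thrombotic risk may be increased by concurrent factor or BPA use. Section 6.3.1.2 lists multiple or repeated doses among the circumstances that may warrant antithrombin replacement. The protocol amendment history shows that Amendment 01 revised the bleed guidelines to mitigate thrombosis risk. The call before a repeat dose belongs to that set of safeguards, so its trigger should read the same wherever patients and sites meet it.

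**Working it through.** This is a comparison of text. No power, alpha, effect size or event count enters it.

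**Step 1: contact thresholds side by side.** The Day 1 to Day 7 instructions for the fitusiran arm are separate and are not compared here.

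| Situation | Bleed management rule | Section 7.2.1 | Result |
|---|---|---|---|
| On-demand arm, BPA | Contact after two doses without adequate hemostasis (6.3.1.1) | Contact if more than two doses are needed | Agree |
| Fitusiran arm from Day 8, rFVIIa | Call before dose 3 (6.3.1.2, Table 4) | Contact if more than two doses are needed | Agree |
| Fitusiran arm from Day 8, aPCC | Call before dose 2 (6.3.1.2, Table 4) | Contact if more than two doses are needed | One dose later |
| Fitusiran arm from Day 8, FVIII and both FIX types | Call before dose 2 (6.3.1.2, Table 4) | No separate rule for these products | One dose later, if the general threshold applies |

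Four of the five product columns in Table 4 differ from Section 7.2.1 by one dose. Three of those four are FVIII and FIX products that are not expected in routine use here, which leaves aPCC as the practical case.

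**Step 2: does another trigger in Section 7.2.1 cover the gap?** Take a fitusiran-arm patient after Day 8 who needs a second aPCC dose. The amount is within the plan and at least 24 hours have passed, which is the Table 4 minimum interval.

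- Higher dose than the plan recommends: not met.
- Higher frequency than the plan recommends: not met on the Table 4 interval.
- More than two doses: not met.

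No contact trigger in Section 7.2.1 applies, although Section 6.3.1.2 and Table 4 make the call mandatory.

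**Step 3: would a described alert detect that dose if no call was made?**

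- Initial-treatment notification: arises from the first treatment and says nothing about a second.
- Contact for an amount above the plan: not met.
- Third-dose alert: not reached.

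The protocol describes no repeat-dose alert at dose 2 and one at dose 3, after administration.

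**The case against.** The strongest reply is that Section 7.2.1 is about recording and notification and does not set the treatment rules. The end of Section 7.2, directly before it, sends bleed management to Section 6.3.1. Fitusiran-arm patients receive a written plan for Day 8 onward, and Section 6.3.1 bases plans on Table 4. The plan is reviewed at clinic visits and at two-weekly contacts, and footnote t of Table 1 includes site-contact requirements in that review. There is also a patient education module, and Section 6.3.1.2 recommends contact before each dose. Nothing in Section 7.2.1 permits a second aPCC dose without a call, and a patient who calls before dose 2 satisfies both sections. The more-than-two-doses wording can be read as a common minimum, with a stricter rule for the fitusiran arm.

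Much of this stands. A reader might infer from Section 7.2.1 that patients would take a second aPCC dose without calling. The documents do not support that prediction, because diary training is not the only instruction patients receive. At most, the wording could mislead. A reader might also infer that the third-dose alert is itself an error. It contradicts no other section: an alert after entry cannot replace a call before dosing, and Section 7.2.1 leaves complete instructions to a Study Manual that was not available. Finally, SAP Section 6.3.3.7 plans a summary of compliance with the bleed guideline after Day 8. A reader might infer that this has no defined standard, but Section 6.3.1.2 and Table 4 agree with each other on this threshold and can serve as one.

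The reply does not remove the inconsistency. Section 7.2.1 states what patients will be instructed to do, names a dose count, and gives no exception by arm or product. The pointer to Section 6.3.1 leaves that sentence as it is.

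**Conclusion.** The inconsistency is real but narrow. It concerns the fitusiran arm from Day 8, and in practice mainly second doses of aPCC, where the two contact thresholds differ by one dose. No alert described in the protocol would detect a second dose taken without the required call. That statement covers the protocol only; the Study Manual may say more.

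The number of affected bleeds cannot be estimated. A reader might size the problem from the planning assumptions: 36 patients × ABR of 4 × 218 days (Day 29 to Day 246) / 365.25 = about 86 bleeds, or 28 × 4 × 218 / 365.25 = about 67 with the evaluable number. These figures count all projected bleeds in the efficacy period, whatever the product and number of doses, and leave out Days 8 to 28, when the call rule already applies. Neither the aPCC share nor the share needing a second dose is given, so neither figure measures the problem.

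The point does not touch the primary analysis. It is worth correcting because the instruction belongs to a thrombosis safeguard and is cheap to align.

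**What to change.** Reconcile Section 7.2.1 with Section 6.3.1.2 and Table 4 so that the patient contact instruction is specific to arm and product and consistent with the bleed management section. A cross-reference in place of the single dose count would be enough. Then confirm that the eDiary alert trigger, and any instruction in the Study Manual, is consistent with the reconciled rule. Which threshold applies is for the sponsor and its clinical advisers to settle.

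The cost is a short wording change in the protocol. An alert configuration change is needed only if the check shows that the current trigger does not fit.

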### 7.3. Pharmacodynamic Assessments

In this study, AT activity level and thrombin generation will be collected as measurements of PD effect. These measurements will be collected and analyzed centrally for research purposes. As interpretation is uncertain, thrombin generation results will not be used to adjust dosing of fitusiran or guide other elements of study conduct or clinical management and will not be shared

---

with sites until after study completion. If clinical circumstances arise for which AT activity levels are required to guide patient care, local laboratory assessments may be drawn.

### 7.3.1. Antithrombin (AT) Activity

AT activity level will be assessed according to the schedule of assessments (Table 1); samples will be collected within 4 hours prior to dosing. Antithrombin levels will be determined by validated assay. Antithrombin protein may be measured in a subset of plasma samples for correlation. Results will be collected and interpreted centrally.

In the fitusiran treatment arm patients who do not enroll in the extension study, following final fitusiran dose, AT activity level will be monitored at monthly intervals until returning to an activity level of approximately 60% (per the central laboratory) or per Investigator discretion in consultation with the study Medical Monitor.

### 7.3.2. Thrombin Generation

Thrombin generation will be assessed according to the Schedule of Assessments (Table 1) using a functional assay per the Laboratory Manual, and will be collected and interpreted centrally.

### 7.3.3. Exploratory Analyses

Except where prohibited by local or national regulations, in consented patients, plasma, serum, and urine samples may be archived and used for analyses of exploratory biomarkers related to the metabolic profiling or effects of fitusiran and for the development of modified thrombin generation assays, and may also be archived for use in other exploratory analyses related to hemophilia and its complications.

In addition, where permitted in consented patients, serum samples may be used for analysis of circulating RNA, including the assessment of cleaved AT RNA, and a sample of DNA may be obtained and archived to permit potential confirmation of hemophilia mutation or genotyping of hemophilia modifier genes or genes that may modify the effects of fitusiran.

## 7.4. Pharmacokinetic Assessments

Blood samples will be collected for assessment of PK including metabolites (as necessary) in all fitusiran arm patients according to the collection schedule presented in Table 7, on the days specified in the Schedule of Assessments (Table 1).

Blood must be aliquoted and processed as plasma for PK analysis. All plasma concentration data (Table 7 and Table 8) will be summarized and analyzed using a population PK approach.

In addition, plasma PK (Table 8, which includes all time points in Table 7) will be evaluated in East Asian patients in the fitusiran arm at East Asian sites (defined as patients from sites in China, Japan, South Korea, and Taiwan), and there will be pooled urine collection for urine PK analysis also in these patients (Table 9).

The concentration of fitusiran will be determined using a validated assay. Full details regarding the processing, shipping, and analysis of the samples will be provided in the Laboratory Manual.

---

## 7.5. Safety Assessments

The assessment of safety during the course of the study will consist of the surveillance and recording of AEs including SAEs, recording of concomitant medication and measurements of vital signs, weight and height, physical examinations, ECG findings, and laboratory tests.

Safety data will be periodically reviewed over the course of the study by the DMC as described in Section 4.6.

### 7.5.1. Vital Signs

Vital signs will be measured as specified in the Schedule of Assessments (Table 1), and will include blood pressure, heart rate, body temperature, and respiratory rate. Vital signs will be measured predose in the seated or supine position, after the patient has rested comfortably for 10 minutes.

Body temperature in degrees Celsius will be obtained via oral, tympanic, or axillary methods. Heart rate will be counted for a full minute and recorded in beats per minute, and respiration rate will be counted for a full minute and recorded in breaths per minute.

For the safety of the patient, additional vital sign assessments may be added at the discretion of the Investigator.

Vital signs results will be recorded in the eCRF.

### 7.5.2. Weight and Height

Height will be measured in centimeters. Body weight will be measured in kilograms. Height and body weight measurements will be collected as specified in the Schedule of Assessments (Table 1) and will be recorded in the eCRF.

### 7.5.3. Physical Examination

Full and directed physical examinations will be conducted as specified in the Schedule of Assessments (Table 1); if a physical examination is scheduled for a dosing visit, it should be conducted prior to dosing.

Full physical examinations will include the examination of the following: general appearance, head, eyes, ears, nose and throat; respiratory, cardiovascular, gastrointestinal, musculoskeletal and dermatological systems; thyroid, lymph nodes, and neurological status.

Directed physical examinations will include the examination of the following systems with attention to evaluation for signs and symptoms of thrombosis, bleeding, and arthropathy: neurologic, chest/respiratory, heart/cardiovascular, dermatological/skin, gastrointestinal/liver, and musculoskeletal/extremities. Other organ systems may be evaluated as indicated by patient symptoms. In patients undergoing a surgical procedure, a directed physical examination will also be performed as specified in the Perioperative Schedule of Assessments (Table 10).

Physical examination notes regarding any observed abnormalities will be recorded on the eCRF.

---

#### 7.5.4. Electrocardiogram

Triplicate standard 12-lead ECGs, with readings approximately 1 minute apart, will be recorded as specified in the Schedule of Assessments (Table 1). Patients should be supine for at least 5 minutes before each ECG is obtained. The electrophysiological parameters assessed will be rhythm, ventricular rate, RR interval, PR interval, QRS duration, QT interval, Bazett-corrected QT interval (QTcB), and Fridericia corrected QT interval (QTcF).

When ECG and blood sample collection occur at the same time, ECGs should be performed before blood samples are drawn.

The Investigator or qualified designee will review all ECGs to assess whether the results have changed since the Baseline visit and to determine the clinical significance of the results. These assessments will be recorded on the eCRF. Additional ECGs may be collected at the discretion of the Investigator. Recordings will be archived according to the Study Manual.

#### 7.5.5. Clinical Laboratory Assessments

The following clinical laboratory tests will be evaluated by a central laboratory. Specific instructions for transaminase elevations are provided in Section 6.2.3.1. For any other unexplained clinically relevant abnormal laboratory test occurring after IMP administration, the test should be repeated and followed up at the discretion of the Investigator until it has returned to the normal range or stabilized, and/or a diagnosis is made to adequately explain the abnormality. Additional safety laboratories and assessments as indicated by the clinical situation may be requested. Clinical laboratory assessments are listed in Table 5 and will be assessed as specified in the Schedule of Assessments (Table 1).

While local laboratory results may be used for urgent clinical and dosing decisions, on the day of the clinic visit assessments, all laboratory assessments specified in Table 5 which are performed at the clinic should also be sent in parallel to the central laboratory. In the case of discrepant local and central laboratory results on samples drawn on the same day, central laboratory results will be relied upon for clinical and dosing decisions.

Clinical laboratory assessments may be collected at the clinical site or at home by a trained healthcare professional. It is preferred that clinical laboratory assessments be drawn via peripheral draw (ie, fresh stick), however in cases where peripheral access is not possible existing indwelling venous access may be utilized.

Please see Section 6.2.3.1 for the LFT monitoring and dosing plan.

**Table 5: Clinical Laboratory Assessments**

Hematology	
Hematocrit	Neutrophils, absolute and %
Hemoglobin	Lymphocytes, absolute and %
RBC count	Monocytes, absolute and %
WBC count	Eosinophils, absolute and %
Mean corpuscular volume	Basophils, absolute and %
Mean corpuscular hemoglobin	Platelet count
Mean corpuscular hemoglobin concentration	CD4 in HIV-positive patients (at Screening only)
Serum Chemistry	
Sodium	Potassium
BUN	Phosphate
Creatinine and eGFR (using the MDRD formula)	Albumin
Glucose	Calcium
Chloride	Carbon dioxide
Liver Function Tests (LFTs)	
AST	ALP
ALT	Bilirubin (total and direct)
GGT	
Coagulation	
Prothrombin time	Activated partial thromboplastin time
INR	Fibrinogen
D-dimer a	Prothrombin fragment 1, 2
Factor Activity	
FVIII activity for patients with hemophilia A	FIX activity for patients with hemophilia B
Urinalysis	
Visual inspection for appearance and color	Bilirubin
pH (dipstick)	Nitrite
Specific gravity	RBCs
Ketones	Urobilinogen
Glucose	Leukocytes
Protein	Microscopy (if clinically indicated)

